### **9.3 Analysis Populations**

Efficacy endpoints will be analyzed in enrolled patients who have baseline and at least one post-baseline measure.

Safety endpoints will be analyzed in enrolled patients who received at least one dose of study drug.

### **9.4 Demographics and Baseline Characteristics**

All baseline patient characteristics of demographic data (age, height, weight, race), disease history, medical history (abnormalities only), physical examination (abnormalities only), and concomitant medications at study entry will be listed for all patients.

Demographic data will be summarized and tabulated. Continuous variables will be summarized using number of observations (n), mean, standard deviation (SD), median, minimum, and maximum. Frequencies and percentages will be reported for all categorical data.

## **9.5 Efficacy Endpoints**

Efficacy endpoints are outlined in the synopsis.

## **9.6 Statistical Methods**

### **9.6.1 Efficacy Analysis**

There are no inferential comparisons for study endpoints. Summary statistical analyses will be performed for all efficacy measures. For proportion based measures, N, frequencies, proportion and its 95% confidence interval (CI) will be produced. For continuous measure, N, mean, median, range, and SD will be produced for observed values, and additional 95% CI for change or percent change from baseline will be produced if applicable.

### **9.6.2 Subgroup Analyses**

Efficacy endpoints will be analyzed on following patient populations. Certain subgroups may be combined when deemed clinically necessary.

- PG EIM
- EN EIM
- psoriasis EIM
- psoriasis due to anti TNF-alpha treatment

Other subgroup analyses based on demographics (such as sex, age, race, etc.) may be performed when deemed appropriate-

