## SYNOPSIS

Name of Drug:	Etrasimod (APD334)
Indication	Inflammatory Bowel Disease (IBD) with active skin extra-intestinal manifestations (EIM) including Psoriasis, Erythema Nodosum (EN), and Pyoderma Gangrenosum (PG)
Sponsor:	Arena Pharmaceuticals, Inc. [name]
Name of Sponsor Contact	██████████ MD CMO Research and Development Arena Pharmaceuticals, Inc. [name] Phone: ██████████ email: ██████████
Name of Principal Investigator(s):	Multi-center
Medical Monitor:	██████████, MD Medical Monitor Arena Arena Pharmaceuticals, Inc. [name] Phone: ██████████ email: ██████████
Test Product, Dose and Mode of Administration:	
 
• ██████████ etrasimod once daily (q.d.) for 12 weeks
 
• Patients should be instructed to take their tablet on an empty stomach (after overnight fast) and to avoid eating for 1 hour after dosing. Patients should be advised not to crush, break, chew, or dissolve the tablet and to take study medication with an adequate amount of water.
 

Concurrent Control:	None. This is an open-label study.
Objectives:	The efficacy objective is to determine the treatment effect of etrasimod in Inflammatory Bowel Disease patients on the clinical improvement of active skin extra-intestinal manifestations. The safety objective is to determine the safety profile and tolerability of etrasimod.
Study Design	This is a phase 2a, proof-of-concept, multicenter, open-label, single-arm study in 10-20 IBD patients with active skin extra-intestinal manifestations. All visits in the study are ambulatory visits. The screening period

will last up to 4 weeks and is followed by a 12-week treatment period. During this treatment period patients will take one tablet of study medication once per day. The last dose is planned to be taken one day before the last treatment visit at week 12. A follow-up visit will take place 2 weeks after the end of treatment.

Study Site(s)	This study will be conducted in approximately 3 clinical centers.

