#### **6.2.1 Prior Therapies**

Prior therapies related to IBD and skin manifestations will be collected during screening.

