#### **6.2.2 History of IBD**

A detailed history of IBD, including date of diagnosis, disease severity, hospitalizations, and extra-intestinal manifestations will be collected during screening.

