## **9 PLANNED STATISTICAL METHODS**

Details of the statistical analyses will be included in a separate statistical analysis plan (SAP) which will be finalized before database lock. If, after database lock, changes are made to the pre-specified statistical analysis plan, the changes will be listed along with an explanation as to why they occurred in the Clinical Study Report.

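### Does the freedom to combine skin subgroups in section 9.6.2 need to be tied down in advance?

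*Combined protocol and SAP*

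**What the plan says.** Section 9.6.2 has the efficacy endpoints analysed in four populations: pyoderma gangrenosum (PG), erythema nodosum (EN), psoriasis, and "psoriasis due to anti TNF-alpha treatment". It then permits pooling: "Certain subgroups may be combined when deemed clinically necessary". It does not say which groups, who decides or when, and no visible sentence says whether the third population contains the fourth.

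Section 9.6.1 sets the summaries. Proportions get a 95% interval, and for continuous measures an "additional 95% CI for change or percent change from baseline will be produced if applicable". Section 9 defers the rest: "Details of the statistical analyses will be included in a separate statistical analysis plan (SAP) which will be finalized before database lock". For changes to that plan after lock, "the changes will be listed along with an explanation as to why they occurred in the Clinical Study Report". Under concurrent control the Synopsis states: "None. This is an open-label study".

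The information needed to class a patient is gathered before dosing. Section 6.2.1 reads "Prior therapies related to IBD and skin manifestations will be collected during screening", and section 6.2.2 reads "A detailed history of IBD, including date of diagnosis, disease severity, hospitalizations, and extra-intestinal manifestations will be collected during screening".

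The size is given as 10 to 20 patients in the Synopsis (study design and statistical analyses entries) and in section 9.2. The Synopsis sample size entry and section 3.1 give a maximum of 20, of whom at most 10 may have anti-TNF psoriasis, and state no minimum.

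**The concern.** Outcomes are visible as they accrue, because nobody is blinded. The separate plan need only be final before database lock, and only later changes must be explained. A pool could therefore be chosen after its results were known, be written into the plan before lock, and carry no mark of how it was chosen. With no control group, the estimate and its interval are all the evidence there is, and the Synopsis intends intervals for key efficacy measures to be set against historical data. A pool selected for its result would have too large a mean and an interval that covers too rarely.

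The psoriasis label adds to the doubt. If the two psoriasis groups are separate, one set of combinations is possible; if one is nested in the other, a smaller set is. The two wordings of the sample size suggest a text that was not fully reconciled.

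**Working it through.** The plan disclaims a formal sample size calculation and gives no SD or effect size, so it has no figure to reproduce. The check asks how much the open wording could cost.

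**Number of pools.** With four separate groups, pools of two or three number C(4,2) + C(4,3) = 6 + 4 = 10. If anti-TNF psoriasis is nested in psoriasis, six new pools remain. Both counts assume one skin diagnosis per patient.

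**Pool chosen without regard to results.** The expected pooled mean equals the true mean. In simulation with all psoriasis fixed in advance, bias is 0.00, coverage 95.0%, and the interval lies wholly on the favourable side of the truth in 2.5% of studies.

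**Pool chosen because its mean is largest.** Assumptions: normal change scores with SD 1, the same true mean in all groups, t-based 95% intervals, 200,000 simulated studies per split. The splits are assumed, since the documents give none. For a choice of two (all psoriasis, with a patients, or PG plus EN, with b patients) there is a closed form:

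bias = √[(1/a + 1/b) / (2π)]

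For 5/5/5/5, a = b = 10, so √(0.2/6.283) = 0.178. For 2/2/6/10, a = 16 and b = 4, so √(0.3125/6.283) = 0.223. For 2/3/3/2, a = b = 5, so √(0.4/6.283) = 0.252. The simulation agrees.

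| Split PG/EN/psoriasis/anti-TNF | Total | Bias, 2 choices (SD) | Bias, 10 choices (SD) |
|---|---|---|---|
| 5/5/5/5 | 20 | 0.178 | 0.296 |
| 3/3/4/10 | 20 | 0.194 | 0.321 |
| 2/2/6/10 | 20 | 0.223 | 0.339 |
| 4/4/4/3 | 15 | 0.206 | 0.344 |
| 2/3/3/2 | 10 | 0.252 | 0.423 |

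With two choices, two-sided coverage stays at 95.0% and the favourable-side miss rate is 4.7 to 4.8%. With ten choices, coverage is 89.5 to 91.0% and the miss rate 8.9 to 10.5%.

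**Yardsticks.** The half-width of a 95% interval for a mean change is t/√n: 2.262/√10 = 0.72 SD at n = 10 and 2.776/√5 = 1.24 SD at n = 5. For the 5/5/5/5 split with two choices, the bias of 0.178 SD is about a quarter of the half-width of the ten-patient pool (0.178/0.715 = 0.25).

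Under the same model, stressing the best of the four planned single groups overstates its mean by 0.46 to 0.66 SD. That is more than any pool does, and it involves no pooling at all. Figures of this kind come with describing very small groups; they do not single out the pooling sentence.

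**The psoriasis label.** Take assumed responders of 2/5 in psoriasis not due to anti-TNF treatment and 7/10 in anti-TNF psoriasis. The psoriasis line reads 2/5 = 40% (exact 95% interval 5% to 85%) if the groups are separate, or (2 + 7)/(5 + 10) = 9/15 = 60% (32% to 84%) if nested. The number changes with the label, but each version follows from the other by adding or subtracting counts. For a mean, the pooled value is (n₁m₁ + n₂m₂)/(n₁ + n₂), and the SD follows from the same reported quantities.

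Separate groups is the natural reading. The two are listed side by side, pooling nested groups would add nothing, and section 1.1.1 treats paradoxical psoriasis on anti-TNF drugs as a process of its own. The enrolment cap also implies that patients are classed on entry.

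**The size wording.** The range 10 to 20 lies inside a maximum of 20, so both can be true. The range carries the only stated minimum; the other wording carries the anti-TNF cap. No computed quantity depends on which is read.

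**The case for a change.** The strongest case for acting is that the criterion in section 9.6.2 is loose, and a judgement of clinical need made by people who have seen the outcomes can drift toward the results without anyone intending it. The absence of an interim analysis (section 9.6.3) does not prevent this in an open-label study. Calling the summaries exploratory does not remove selection bias from a mean or an interval. Naming one pool, such as all psoriasis, would cost a sentence or two, forbid nothing, and match the population of the psoriasis severity endpoint.

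Much of this stands. The text is open as described, the arithmetic is right, and whoever writes the separate plan could well name that pool. But the case for requiring a change depends on replacing the written rule with one that always reports the largest mean. The upper figures also count pools such as PG with anti-TNF psoriasis, for which the documents suggest no clinical reason. The separate plan, which is not in the text reviewed, may already settle both the pools and the psoriasis label.

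The obvious repairs bring problems of their own. Declaring that none of the four groups overlap has no support, because inclusion criterion 5 does not limit a patient to one skin diagnosis. Replacing the 10-to-20 range with the maximum alone would delete the only stated minimum.

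**Conclusion.** The concern describes the text correctly but calls for no change. Section 9.6.2 leaves out detail that analysts can be expected to supply: treat the two psoriasis groups as separate, and show any clinically motivated pool beside the four groups that are analysed anyway. Followed as written, the pooling rule has no bias.

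The possible overstatement, 0.18 to 0.25 SD with two plausible pools and 0.30 to 0.42 SD with all ten, is an upper range. It assumes selection purely on results, equal true means, normal data, one skin diagnosis per patient and the group sizes shown above.

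No decision rule depends on it. The Synopsis calls every endpoint exploratory, section 9.1.2 specifies no tests, section 9.6.1 makes no inferential comparisons, and the comparison with historical data is described as non-inferential. The psoriasis label is recoverable from the reported groups, and the two statements of size are compatible.

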### **9.6.3 Interim Analysis**

No interim analyses are planned for this study.

## 9.7 Safety Analysis

Safety and tolerability will be assessed by a review of all safety parameters including adverse experiences (AEs), laboratory safety parameters, vital signs, and ECG. Adverse experiences will only be presented as summary tabulations. When assessing change from baseline, a baseline measurement is also required. Baseline for the safety analysis is defined as the last pre-dose measurement. No missing data will be imputed for the safety analysis. For continuous variables, summary statistics (N, mean [or median], SD, mean [or median] change/percent change) and 95% CI will be produced if applicable; for proportion based measures, N, frequencies, proportion and its 95% CI will be produced.

### 9.7.1 Adverse Events

Adverse events will be coded using the most current Medical Dictionary for Regulatory Activities (MedDRA) and tabulated, including categorical information of interest such as onset and resolution times, time of onset relative to dose, severity at onset, maximum severity, causal relationship to study medication, and action taken. AEs will be regarded as 'pre-treatment' if they occur between Screening and the time of administration of the first dose of etrasimod. All other AEs that occur after the first dose of study medication will be considered to be 'treatment-emergent'.

Pre-treatment and Treatment-emergent AEs will be listed by patients, in terms of seriousness, severity and Intensity (assessed according to the Common Terminology Criteria for Adverse Events v4.0313 definitions). TEAEs will be classified according to system organ class.

### 9.7.2 Physical Examinations

Physical examination results (abnormalities only) at each study visit will be listed.

### 9.7.3 Concomitant Medication

[figure not shown]
Pre-treatment and concomitant medication administered during the study will be listed. Concomitant medications will be coded using the WHODRUG Dictionary.

### 9.7.4 Vital Signs

Individual vital sign measurements will be summarized using descriptive statistics. Summary statistics will also be provided for change from baseline in vital sign measurements. Baseline is defined as the last pre-dose measurement.

### 9.7.5 Clinical Laboratory Values

Individual lab values will be listed by visit, and summarized using descriptive statistics. Summary statistics will also be provided for change from baseline in lab values. Baseline is defined as the last pre-dose measurement. A clinically significant change from baseline may be recorded as an AE if deemed appropriate by the PI or sponsor.

### 9.7.7 Lymphocyte counts

Absolute lymphocyte counts at specified time points will be listed for each patient and will be summarized by dose level. The relationship between clinical efficacy and lymphocyte count lowering will be assessed.

## **10 REGULATORY REQUIREMENTS**

### **10.1 Pre-Study Documentation:**

The sponsor must receive the following documentation prior to initiation of the trial:

- Protocol signature page signed and dated by the principal investigator (PI)
- FDA form 1572 signed and dated by all PIs
- Curriculum vitae of the PI and subinvestigators, updated within 2 years
- Current medical licenses for the PI and all subinvestigators
- Financial disclosure form signed by the PI and all subinvestigators listed on the FDA Form 1572 (USA only)
- Copy of the IRB/IEC approval letter for the study and approved ICF
- IRB/IEC Membership List

Additional country specific documentation may be required per international regulatory authorities.

### **10.2 Investigator Obligations**

The PI is responsible for ensuring that all study site personnel, including subinvestigators and other study staff members, adhere to all country regulatory requirements and guidelines regarding clinical trials, including guidelines for GCP (including the archiving of essential documents), both during and after study completion. The PI will be responsible for the patient's compliance to the study protocol. The PI is responsible for providing the sponsor an adequate final report shortly after he/she completes participation in the study, in accordance with ICH Guidelines E6, E2A, and E8.

### **10.3 Patient Confidentiality**

All information obtained during the conduct of the study with respect to the patients' state of health will be regarded as confidential. This is detailed in the written information provided to the patient. An agreement for disclosure of any such information will be obtained in writing and is included in both copies of the ICF signed by the patient. The study data shall not be disclosed to a third party without the written consent of the sponsor.

### **10.4 Informed Consent**

According to the ICH guideline for GCP (E6), the investigator will obtain and document informed consent for each patient screened for this study. All patients will be informed in writing of the nature of the protocol and investigational therapy, its possible hazards, and their right to withdraw at any time, and will sign a form indicating their consent to participate prior to the initiation of study procedures. The patient's medical record should contain

written documentation indicating that informed consent was obtained. The ICF must be reviewed and approved by the investigator's designated IRB/IEC and by the sponsor. The ICF should include all the elements as outlined in Section 4.8.10 of the ICH guideline for GCP (E6).

## **10.5 Institutional Review Board**

This protocol and relevant supporting data are to be submitted to the appropriate IRB/IEC for review and approval before the study can be initiated. Amendments to the protocol will also be submitted to the IRB/IEC prior to implementation of the change. The sponsor must receive a letter documenting the IRB/IEC approval prior to initiation of the study. The PI is also responsible for informing the IRB/IEC of the progress of the study and for obtaining annual IRB/IEC renewal. The IRB must be informed at the time of completion of the study and should be provided with a summary of the results of the study by the PI. The PI must notify the IRB/IEC in writing of any SAE or any unexpected AE according to ICH guidelines.

## **11 PROTOCOL MANAGEMENT AND ADMINISTRATIVE CONSIDERATIONS**

### **11.1 Study Documentation**

The PI and study staff has the responsibility of maintaining a comprehensive and centralized filing system containing all study-related documentation. These files must be available for inspection by the sponsor, representatives of the sponsor, the IRB/IEC, and regulatory authorities (i.e., FDA or international regulatory authorities) at any time, and should consist of the following elements:

Patient files, containing the completed case report forms (CRFs), supporting source documentation from the medical record including laboratory data and the ICF; Regulatory files, containing the protocol with all amendments and investigator signature pages, copies of all other regulatory documentation, and all correspondence between the site and the IRB/IEC and sponsor; and Drug accountability files, including a complete account of the receipt and disposition of the study medication (test article).

Records are to be available for 2 years after marketing application approval, or if the application is not approved or never submitted, 2 years after the last shipment and delivery of the material and the appropriate competent regulatory authorities are notified. The sponsor will provide written notification when it is appropriate for the investigator(s) to discard the study-specific documents referenced above.

### **11.2 Protocol Interpretation and Compliance**

To ensure accurate interpretation and implementation of the study, the procedures and endpoints defined in the protocol will be carefully reviewed by the PI and his or her staff prior to the time of study initiation. The sponsor and PI will follow all reasonable means to resolve any differences of opinion of matters of eligibility, toxicity and other endpoints. In the event that a resolution cannot be reached then one or both parties may seek to terminate the study following the provisions outlined in the Clinical Trials Agreement.

### **11.3 Study Monitoring**

The sponsor or a contracted monitor will visit the study center periodically to monitor adherence to the protocol, compliance with ICH guidelines, adherence to applicable FDA regulations, and the maintenance of adequate and accurate clinical records. Case report forms will be reviewed to ensure that key safety and efficacy data are collected and recorded as specified by the protocol. The monitor will be permitted to access patients' complete medical records, laboratory data, and other source documentation as needed to monitor the trial appropriately.

**Arena Pharmaceuticals, Inc. Signatures:**

## Appendix 1 Progressive Multifocal Leukoencephalopathy (PML) Checklist

Symptoms	“Compared to how you usually feel, have you had a significant change in any of the following?”		If the answer is “yes”, obtain a description of the symptom(s) with examples.	Applicable Objective Test(s): Document results on PML Object Checklist
	Yes	No		
1) Have you been experiencing any persistent difficulty with your vision such as loss of vision or double vision? Have you been having trouble reading?				Test visual fields and ocular motility
2) Have you been experiencing any persistent difficulty speaking or having your speech understood by others?				Casual observation of speech output for dysarthria or aphasia. Ask patient to name a few objects and repeat a multipart phrase.
3) Have you been experiencing any persistent weakness in an arm or leg?				Test for pronator draft (Barre maneuver) and/or fixation on arm roll, Assess the ability to hop on either foot; foot and finger tapping. Test muscle strength.
4) Have you noticed yourself regularly bumping into things or having difficulty writing?				Ask for spontaneous writing sample and observe finger to nose, heel to shin, and tandem gait.
5) Have you regularly been experiencing difficulty understanding others?				Ability to follow serial commands
6) Have you had persistent problems with your memory or thinking?				Recall of 3 objects over 1 minute to distraction; ability to follow commands.
7) Have you been experiencing any persistent numbness or other loss of sensation?				Test sensation side to side with pinprick.
